**Figure 5: Prophylactic efficacy of the Sm-p80 vaccine in baboons.**

### 2.1.4 Safety of GLA-SE

The 5 µg dose of GLA-SE to be used in this trial is comfortably in the mid-range of tested doses of the adjuvant and has been shown to be safe and well tolerated in hundreds of human subjects.

#### Preclinical Safety

As reported in the GLA-SE Investigator Brochure (v5, March 2016) many preclinical and nonclinical studies in mice, guinea pigs, rats, rabbits, and non-human primates have demonstrated the immunostimulatory properties of GLA-SE with no significant safety signals.

Thousands of mice have been immunized with candidate antigens for infectious disease vaccines (e.g., leishmaniasis, tuberculosis, leprosy, malaria, influenza) formulated in GLA-SE. No safety issues have been observed when the following parameters were evaluated: clinical observations including general health and mortality; injection site reactions; body weights; food consumption; and, gross pathology. In addition, the potential for auto-antibody generation following GLA

---

administration was evaluated through extensive immunohistochemistry assays for immune complexes and/or autoimmune pathology, and no signs of detrimental autoimmune effects were found. Studies have also assayed for anti-nuclear antibody and have not found abnormal levels in GLA-immunized mice.

More than 300 guinea pigs have been immunized with candidate tuberculosis vaccine antigens formulated with GLA. Again, no safety issues have been observed when the following parameters were evaluated: clinical observations including general health and mortality; injection site reactions; body weights; food consumption; and, gross pathology. In addition, a safety study was conducted in guinea pigs in which various GLA adjuvant formulations (oil-in-water emulsions, aqueous suspensions, liposomes) were administered without antigen by three different injection routes (subcutaneous, intramuscular [IM], and intradermal). Administration of GLA-SE by all three routes appeared to be safe and well tolerated.

GLA-SE has been tested in several safety, immunogenicity, and/or efficacy studies in nonhuman primates. The safety parameters evaluated included clinical observations, injection site evaluations, body weights, body temperatures, hematology, coagulation, clinical chemistry, and immunogenicity. In each study the adjuvant was safe, well tolerated, and increased the immune response to the co-administered antigen. No treatment-related adverse effects were observed in the safety parameters evaluated except for mild injection site reactions and a mild, transient acute phase inflammatory response characterized by increases in C-reactive protein (CRP), fibrinogen, and neutrophils.

GLA-SE has been tested in several toxicity studies in rabbits and rats conducted under GLP guidelines. Parameters evaluated included the following: morbidity/mortality; clinical signs; injection site reactogenicity; body weights; body temperatures; food consumption; ophthalmologic evaluations; clinical chemistry; hematology; coagulation; gross necropsy observations; organ weights; histopathology; and, immunogenicity. In these studies, GLA-SE was found to be safe, well tolerated, and immunostimulatory. No treatment-related adverse effects were observed in the parameters evaluated except for reversible injection site reactions (erythema, edema, inflammation) and a mild, transient acute inflammatory response (changes in hematologic values, increased fibrinogen levels) in some animals receiving GLA adjuvant formulations.

## **Clinical Experience**

GLA-SE has been evaluated in numerous completed or ongoing clinical trials. These trials have investigated GLA-SE formulated with antigens, including recombinant antigens, developed for vaccines against a wide variety of diseases, including leishmaniasis,[15] tuberculosis,[16,17] influenza,[18,19] schistosomiasis,[20] and malaria[21]. These clinical trials have evaluated

---

GLA-SE at 0.5, 1, 2, 2.5, 5, 10, or 20 µg dose levels. In these studies, over 1100 subjects have received at least one study injection containing GLA-SE. Safety data have not revealed any significant safety issues at any dose level tested. These studies have revealed a generally acceptable safety profile:

- Study injections are generally well tolerated;
- There have been no serious adverse events (SAEs) related to study injection;
- Injection site reactions are common and may include pain, tenderness, erythema, and induration;
- Systemic reactions may include headache, fatigue, anorexia, fever, chills, myalgia, and arthralgia;
- Transient elevations in CRP levels were noted in a study of GLA-SE administered with the Fluzone influenza vaccine; and
- Hematologic changes may occur (including decreases in hemoglobin, WBC, and neutrophils).

These reactions varied from study to study, were generally mild, resolved quickly, and are typical of vaccinations by the IM route. GLA-SE often increases the rate and severity of local and systemic reactogenicity compared to the antigen alone. This is consistent with the nonclinical animal experience and is to be expected of a potent immunostimulant.

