Expected AEs associated with GLA-SE administration include injection site reactions that may include pain, tenderness, erythema and induration, systemic reactions that may include headache, fatigue, anorexia, fever, chills, myalgia, and arthralgia. Transient hematologic changes have been observed in preclinical evaluations and in human clinical trials, including decreases in hemoglobin, WBC, and neutrophils. Transient elevations of CRP have been noted in preclinical evaluations and in one human clinical trial, in which GLA-SE was formulated with the Fluzone influenza vaccine.

---

Acute and potentially life-threatening allergic reactions, such as anaphylaxis, are also possible. These reactions occur in about 1 in 4 million people given a vaccination. These reactions can manifest as skin rash (hives), swelling around the mouth, throat, or eyes (angioedema), difficulty breathing (bronchospasm), a fast pulse (tachycardia), or decrease in blood pressure (hypotension). If these reactions occur, they can usually be stopped by the administration of emergency medications by the study personnel. As with any vaccine or medication, there is a very small chance of a death, although researchers do not expect this to occur.

Subjects will be asked to provide protected health information (PHI). All attempts will be made to keep this PHI confidential within the limits of the law. However, there is a chance that unauthorized persons will see the subject's PHI. All study records will be kept in a locked file cabinet or maintained in a locked room at the study site. Electronic files will be password-protected. Only people who are involved in the conduct, oversight, monitoring, or auditing of this trial will be allowed access to the PHI that is collected. Any publications from this trial will not use information that will identify subjects by name. Organizations that may inspect and/or copy research records maintained at the participating sites for quality assurance and data analysis include groups such as the local IRB, NIAID, and the FDA.

A description of this clinical trial will be available on <http://www.ClinicalTrials.gov>, as required by US Law. This web site will not include information that can identify subjects.

There may be other risks, discomforts, or side effects that are unknown at this time.

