## 3.3 Study Endpoints or Outcome Measures

### 3.3.1 Primary

- Occurrence of study vaccine-related SAEs from the time of the first study vaccination through approximately 12 months after the last study vaccination.
- Occurrence of solicited injection site and systemic reactogenicity events from the time of each study vaccination through 7 days after each study vaccination.
- Occurrence of clinical safety laboratory AEs from the time of each study vaccination through approximately 28 days after each study vaccination.
- Occurrence of all unsolicited AEs, regardless of the assessment of seriousness or relatedness, from the time of each study vaccination through 28 days after each study vaccination.
- Occurrence of SAEs, MAAEs, NOCMCs, and PIMMCs from the time of the first study vaccination through approximately 12 months after the last study vaccination.

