## 7.2      **Laboratory Evaluations**

### 7.2.1      **Clinical Laboratory Evaluations**

Subjects will be screened for HIV-1 and HIV-2 infection by a fourth-generation testing algorithm, for HCV infection, and for HBsAg. Screening labs also include WBC, hemoglobin, platelets, creatinine, and ALT.

Serum (screening visit) and urine (study product injection visits) pregnancy tests will be performed. Serum pregnancy tests will be performed by the Quest clinical diagnostic laboratory. Urine pregnancy CLIA-waved tests will be performed by research staff at the research site specimen processing laboratory. Pregnancy testing will be done at the screening visit and within 24 hours prior to each study product injection on all women of childbearing potential. Results must be negative and known prior to enrollment on Day 1 and administration of each study product injection.

Clinical safety laboratory parameters (WBC, hemoglobin, platelets, ALT, and creatinine) will be collected from each subject on the day of and prior to each study product injection, approximately 7 days after each study product injection, and approximately 28 days after each study product injection (which may also serve as the clinical safety laboratory samples for the second and/or third study product injection). These evaluations will be performed by the Quest laboratory. Venous blood samples will be collected for these safety labs. The results from the clinical safety laboratory parameters collected on the day of study product injections will not be available or reviewed prior to study product injection.

Laboratory values that are outside the range of eligibility but are thought to be due to an acute condition or due to laboratory error may be repeated once. One or more of the laboratory parameters may be repeated at any time during the study as determined by the PI, if indicated by an AE. A clinically significant abnormal value should be repeated within 10 days if possible and followed up as clinically relevant.

The volume of venous blood to be collected for the clinical safety laboratory evaluations is presented in Table 8 and Table 9.

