## 8 ASSESSMENT OF SAFETY

### 8.1 Assessing and Recording Safety Parameters

Safety will be assessed by the frequency and severity of:

1. SAEs occurring from the time of the first study product injection through the end of follow-up which is approximately 12 months after the last study product injection.
2. Solicited AEs – reactogenicity events occurring from the time of each study product injection through 7 days after each study product injection:
  - a) Injection site reactions including pruritus, erythema, induration/swelling, pain, and tenderness.
  - b) Systemic reactions including fever, chills, fatigue, malaise, myalgia, arthralgia, headache, nausea, and vomiting.
3. Clinical safety laboratory AEs assessed as described in [Section 7.2.1](#). Parameters to be evaluated include WBC, hemoglobin, platelets, ALT, and creatinine.
4. Unsolicited AEs – non-serious AEs occurring from the time of each study product injection through 28 days after the study product injection.
5. MAAEs, NOCMCs, and PIMMCs occurring from the time of the first study product injection through the end of follow-up which is approximately 12 months after the last study product injection.

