## **8.5 Procedures to be Followed in the Event of Abnormal Laboratory Test Values or Abnormal Clinical Findings**

The site PI or appropriate co-investigator is responsible for reporting all AEs/SAEs that are observed or reported during the study, regardless of the relationship to study product. AEs/SAEs, abnormal clinical laboratory test values, or abnormal clinical findings will be documented, reported and followed appropriately.

Clinical safety laboratory results from specimens obtained after the first study product injection will be graded as indicated in the Toxicity Tables in [Appendix C](#). Clinical laboratory evaluations assessed on the day of and prior to the first study product injection (Day 1) will be considered as baseline.

Systolic and diastolic blood pressures obtained following vaccination will be defined as AEs and graded as indicated in the Toxicity Tables in [Appendix C below](#). However, baseline values prior to the first vaccination, including values obtained at the screening visit and at Visit 1 prior to vaccine administration, may meet the inclusion criteria of systolic blood pressure 85 to 150 mmHg, inclusive, but fall within values defined as Grade 1 severity in the Toxicity Table. Similarly, baseline values may meet the inclusion criteria of diastolic blood pressure  $\leq$  100 mmHg but fall within values defined as Grade 1 severity in the Toxicity Table. For those participants with baseline blood pressure values that are defined as Grade 1 in the Toxicity Table, subsequent, post-vaccination, values will not be defined as an AE unless the post-vaccination value meets the criteria for Grade 2 or 3 and therefore represents a change from baseline. Those values that represent a change from baseline will be defined as Grade 1 AEs for the Grade 2 values and Grade 2 AEs for the Grade 3 values as they represent a change of one two grades from baseline, respectively.

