4.5.1. Safety Variables

Serious adverse events (SAEs) will be assessed from the time of the first study product injection through the end of the follow-up which is approximately 12 months after the last study product injection.

Solicited adverse events (AEs) will document reactogenicity events occurring from the time of each study product injection through 7 days after each study product injection. Injection site reactions of interest include pruritus, erythema, induration/swelling, pain, and tenderness. Systemic reactions of interest include fever, chills, fatigue malaise, myalgia, arthralgia, headache, nausea, and vomiting.

Unsolicited AEs will document non-serious AEs occurring from the time of each study product injection through 28 days after the study product injection.

Clinical safety laboratory AEs will be collected on the day of and prior to each study product injection, approximately 7 days after each study product injection, and approximately 28 days after each study product injection (which may also serve as the clinical safety laboratory samples for the second and/or third study product injection). Parameters to be evaluated include white blood cells (WBC), hemoglobin, platelets, alanine aminotransferase (ALT), and creatinine.

MAAEs, NOCMCs, and PIMMCs will be assessed from the time of the first study product injection through the end of the follow-up period, which is approximately 12 months after the last study product injection.

All solicited and unsolicited AEs and laboratory values are graded on a scale of 0 (absent), 1 (mild), 2 (moderate), and 3 (severe) according to toxicity grading scales ([Table 6](#), [Table 7](#)).

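### The safety panel has no neutrophil count although neutrophil falls were seen with GLA-SE in humans, and WBC 3.51–3.79 is below the eligibility limit yet carries no grade

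*Protocol*

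**What the plan says.** Two Protocol sections describe blood-count effects of the adjuvant. Section 2.1.4 (Clinical Experience) states that "Hematologic changes may occur (including decreases in hemoglobin, WBC, and neutrophils". Section 2.3.1 is the firmer statement: "Transient hematologic changes have been observed in preclinical evaluations and in human clinical trials, including decreases in hemoglobin, WBC, and neutrophils". Groups B to E, nine subjects each, receive GLA-SE.

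The panel is fixed in Protocol section 7.2.1: "Clinical safety laboratory parameters (WBC, hemoglobin, platelets, ALT, and creatinine) will be collected from each subject". Section 8.1 repeats it: "Parameters to be evaluated include WBC, hemoglobin, platelets, ALT, and creatinine". SAP sections 4.5.1 and 9.6 and both schedules of events have the same five parameters. No differential or neutrophil count is collected, graded or tabulated anywhere.

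A primary endpoint (Protocol section 3.3.1) is "Occurrence of clinical safety laboratory AEs from the time of each study vaccination through approximately 28 days after each study vaccination". Under Protocol section 8.5, "Clinical safety laboratory results from specimens obtained after the first study product injection will be graded as indicated in the Toxicity Tables". SAP section 4.5.1 adds that "laboratory values are graded on a scale of 0 (absent), 1 (mild), 2 (moderate), and 3 (severe".

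Inclusion criterion 10 (Protocol section 5.1.1, SAP section 4.3) sets the protocol's normal WBC range at 3.80 to 13.00 × 10³/UL. Appendix C and SAP Table 7 set Grade 1 WBC decrease at 2.50–3.50, Grade 2 at 1.50–2.49 and Grade 3 below 1.50.

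**The concern.** The trial is first-in-human for this vaccine, and its sample-size section says the purpose is to detect AEs related to the product. The Protocol names three blood-count falls seen with the adjuvant; two are measured and the third is not, with no reason given. An asymptomatic neutrophil fall with total WBC still above 3.50 would produce no laboratory AE, and the scheduled results would not show it to the investigator or the SMC.

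The WBC boundary is a smaller, separate matter. A subject eligible at 3.80 or above who drops to 3.6 has left the protocol's own normal range but has no grade. On the SAP's 0-to-3 scale that result goes in the None column of Table 68. In Table 67 it does so too, unless another hematology parameter is graded.

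**Working it through.** **1. The plan's own figure.** Protocol section 10.2 and SAP Table 4 give the chance of at least one event, 1 − (1 − p)ⁿ. For p = 0.20 and n = 9, 1 − 0.80⁹ = 0.866, as stated; the other entries also reproduce.

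**2. Detection if neutrophils were counted.** The same formula applies to a graded neutrophil fall with true rate p. The 36 adjuvanted subjects are pooled on the assumption of a common rate.

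| p | n = 9 | n = 36 |
|---|---|---|
| 0.05 | 0.370 | 0.842 |
| 0.10 | 0.613 | 0.978 |

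As written, the scheduled panel cannot detect an isolated fall that leaves WBC ungraded.

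**3. Can total WBC stand in?** The documents give no neutrophil share. Assume a share f of 50–70% and that only neutrophils fall. From baseline W, WBC reaches 3.50 when neutrophils reach 3.50 − W(1 − f). The required fall is 1 − [3.50 − W(1 − f)]/(Wf).

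| Baseline WBC | f = 50% | f = 60% | f = 70% |
|---|---|---|---|
| 5.0 | 60% | 50% | 43% |
| 7.0 | 100% | 83% | 71% |
| 10.0 | never | never | 93% |

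Example: W = 7.0, f = 60% gives 4.2 neutrophils and 2.8 other cells. Neutrophils must reach 0.7, and 1 − 0.7/4.2 = 83%. For Grade 2 (2.49 or lower) at this baseline, losing every neutrophil at f = 60% leaves 2.8, still Grade 1. At f = 70% they must reach 2.49 − 2.1 = 0.39, and 1 − 0.39/4.9 = 92%.

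**4. Do eligibility and Grade 1 limits meet?**

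| Laboratory parameter | Eligible | Grade 1 begins |
|---|---|---|
| WBC, high | ≤ 13.00 | 13.01 |
| Hemoglobin, female | ≥ 11.5 | 11.49 |
| Hemoglobin, male | ≥ 12.6 | 12.5 |
| Platelets, low | ≥ 131 | 130 |
| Platelets, high | ≤ 415 | 416 |
| ALT | < 47 | 47 |
| Creatinine | ≤ ULN | > ULN |
| **WBC, low** | **≥ 3.80** | **3.50** |

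Only WBC low leaves a gap: 3.51 to 3.79, or 29 values at 0.01 resolution. From a baseline of 3.80, a 7.6% fall (to 3.51) is ungraded and a 7.9% fall (to 3.50) is Grade 1.

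**5. Size of the gap.** The documents give no WBC distribution. If values were normal with mean 5.5–7.0 and SD 1.3–1.9, between 0.3% (7.0, 1.3) and 3.8% (5.5, 1.9) of single values would lie in it before any vaccine effect. This treats subjects as unselected, although all had at least 3.80 at screening.

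**6. Draws concerned.** SAP Table 8 lists post-dose safety draws on Days 8, 29, 36, 57, 64 and 85 in Groups A, B, D and E (six), and on Days 8, 29, 36, 57, 180, 187 and 208 in Group C (seven). Day 180 is 151 days after dose 2, outside the endpoint's window of about 28 days. Six draws per subject therefore count in every group.

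**The case against.** The strongest case against the point is that the WBC part has little consequence, and much of that stands.

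- A reader might infer that the gap weakens the stopping rules. It does not: the lowest laboratory grade in Protocol sections 8.6.1 to 8.6.3 is Grade 2.
- A reader might infer that white-cell falls cannot be registered at all. They can: WBC of 3.50 or lower is graded. In the final report, values in the gap enter the summaries in SAP Table 75 and the mean changes in Figure 23, and Listing 14 shows each one. An investigator may also report an abnormal laboratory finding as an AE (Protocol section 8.1.1). One limit remains: the interim set in SAP section 6.2 includes Table 68 but none of those three displays.
- A reader might take it that every graded limit except WBC meets its eligibility limit. That holds for laboratory parameters only. Grade 1 blood-pressure bands lie inside the eligible range, and Protocol section 8.5 handles that overlap with a baseline rule, so differing limits are not errors in themselves.

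On neutrophils, section 2.1.4 says the changes may occur and calls the reactions generally mild and quickly resolved. Section 2.3.1 places them in the expected-AE paragraph but in a separate sentence. The non-human primate data in section 2.1.4 show neutrophil increases. It is therefore too strong to say that the plan predicts neutrophil falls here. That bears on how serious the omission is; it does not supply a measurement.

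**Conclusion.** The point holds in two parts of unequal weight.

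The neutrophil part is the one to act on. The Protocol reports neutrophil falls with GLA-SE in human trials, and 36 of 45 subjects receive it, yet the primary laboratory endpoint has no means of recording an isolated fall. Total WBC is a weak proxy, especially at mid-range or high baselines. That judgment rests on the assumed 50–70% share and on only neutrophils falling; it illustrates insensitivity and does not forecast an effect.

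The WBC part is minor: a 0.29-wide band at the mild edge is counted as None, which slightly under-counts Grade 1 laboratory AEs. The 0.3–3.8% range rests on assumed distributions. It might also be inferred that the under-count falls mainly in the adjuvanted groups, but no figure in the documents supports that.

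**What to change.** 1. Reconcile the lower WBC eligibility limit with the upper Grade 1 limit so that they meet, as for the other laboratory parameters. The places are Protocol section 5.1.1 criterion 10 and Appendix C, and SAP section 4.3 and Table 7. Which limit moves is for the sponsor.
2. Have the laboratory report the automated differential from the EDTA tube already drawn at each safety visit, and add absolute neutrophil count to the SAP hematology displays (Tables 58 and 67–77, Listing 14). The sponsor decides its grades and whether they feed the escalation and halting rules.
3. SAP sections 9.3.1 and 9.7 describe some assessments in the past tense. If the draws are complete, state in the clinical study report that neutrophils were not assessed.

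The cost is a laboratory fee, presumably small (the documents give none), some additional table shells and a few more Grade 1 laboratory AEs, with no extra visit or blood. If neutrophil grades feed the rules, there may also be extra SMC reviews or pauses: under Protocol section 8.6.3, one related Grade 3 laboratory AE, or the same related Grade 2 or higher laboratory AE in three subjects, brings in the SMC. Under the Protocol Summary, meeting these criteria at a dose-escalation review pauses all vaccination.
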